4.2. SCIENTIFIC RATIONALE FOR STUDY DESIGN

The randomized, double-blind, placebo-controlled, parallel-group trial is the optimal design for evaluation of efficacy and safety of an investigational drug. The 6-month duration of the treatment period is considered sufficient to demonstrate a sustained superiority of DCR-PHXC as compared with placebo in lowering Uox in patients with PH.

The primary endpoint of this Phase 2 study will be 24-hour urinary oxalate excretion, measured as the AUC of percent change from baseline over the last 3 months of treatment. This endpoint is proposed in order to assess a reduction in oxalate burden over time rather than at a single time point at the end of study (EOS). The Sponsor believes the biological relationship between urinary oxalate supersaturation and the subsequent calcifications in kidney and extra-renal organs has been well established. The degree of hyperoxaluria predicts the development and severity of nephrocalcinosis and is an independent risk factor for ESRD in patients with PH ([Zhao et al., 2016](#)). In order to demonstrate a substantial change from baseline in 24-hour Uox in patients with highly elevated Uox levels, a population of patients with at least one baseline Uox value ≥ 1.6 mmol/24 hours will be enrolled and analyzed in a subgroup analysis.

4.3. JUSTIFICATION FOR DOSE

The safety margins for this study were calculated based on the no observed adverse effect levels (NOAELs) determined in the chronic toxicity studies in mice and monkeys and the supporting pharmacology data in non-GLP exploratory studies (see the IB for additional details).

4.3.1. PK/PD Model for Dose Selection in Adults and Adolescents

In the Phase 1 study (Study No. DCR-PHXC-101), single doses of DCR-PHXC have been administered to patients with PH1 or PH2 at either 1.5, 3.0, or 6.0 mg/kg and to healthy volunteers in the dose range of 0.3 to 12 mg/kg.

A preliminary PK/PD M&S analysis explored the relationship between model-predicted DCR-L1360 plasma concentrations and 24-hour Uox concentrations in patients with PH. The PK model was developed using the PK data from both healthy volunteers (N=15) and patients with PH (N=10). The PK-PD model only involved the PD data from patients with PH. The model fits were evaluated using several diagnostic plots and further qualification was done using prediction corrected visual predictive check (pcVPC). The model adequately described the observed data, with an even distribution of observations above and below the 10th and 90th prediction intervals. From the data available, the predictive performance of the model was considered acceptable. Various simulations were conducted to optimize both the dose and dosing regimen to predict the proportion of participants with a 24-hour Uox < 0.6 mmol/24 hours (near-normal range) and < 0.46 mmol/24 hours (normal range).

From these simulations, a dose of 170 mg administered monthly was selected for adults and for adolescents weighing at least 50 kg. For adults and adolescents weighing less than 50 kg, a lower dose of 136 mg was selected.

4.3.2. PK/PD Model for Dose Selection in Children Younger than 12 Years of Age

The preliminary PK-PD model that was developed using the adult and adolescent data from the DCR-PHXC-101 study was updated to include data from studies DCR-PHXC-102, DCR-PHXC-103, all available adult data from Study DCR-PHXC-301, and at least 3 adolescents from the DCR-PHXC-201 and DCR-PHXC-301 studies. The model fits were evaluated using several diagnostic plots and further qualification was done using pcVPC. The model adequately described the observed data, with an even distribution of observations above and below the 10th and 90th prediction intervals. From the data available, the predictive performance of the model was considered acceptable.

The dose selection for the 6- to 11-year-old participants was based on PK and PK-PD simulations. The dose was selected such that the 6- to 11-year-old participants will have a similar exposure to DCR-PHXC as participants receiving the 170 mg dose and to provide for a comparable proportion of participants with normal or near-normal levels of 24-hour Uox. Based on these simulations, a dose regimen of 3.5 mg/kg once monthly was selected. Note: the total dose administered in 6- to 11-year-old participants will not exceed 136 mg.

4.3.3. Placebo Comparator

Normal saline for injection is of a similar osmolality to DCR-PHXC and is approved for SC injection.

4.4. END OF STUDY DEFINITION

A participant is considered to have completed the study if he or she has completed all phases of the study including the last visit or the last scheduled procedure shown in the Schedule of Activities (SoA), Section 1.3.

The end of the study is defined as completion of the last visit or procedure shown in the SoA in the trial globally.

5. STUDY POPULATION

5.1. INCLUSION CRITERIA

In order to be eligible to participate in this study, an individual must meet all of the following criteria:

Age

1. At least 6 years of age, at the time of signing the informed consent/assent

Type of Participant and Disease Characteristics

2. Documented diagnosis of PH1 or PH2, confirmed by genotyping (historically available genotype information is acceptable for study eligibility)
3. 24-hour Uox excretion ≥ 0.7 mmol (adjusted per 1.73 m^2 BSA in participants < 18 years of age) in both collections performed in the screening period. At least 12 participants must have at least one 24-hour Uox excretion ≥ 1.6 mmol (adjusted per 1.73 m^2 BSA in participants aged < 18 years).
4. Less than 20% variation between the two 24-hour urinary creatinine excretion values obtained in the screening period. Individuals who do not achieve $< 20\%$ variation between the 2 screening values may undergo a second round of urine collection. An extra 7 calendar days may be added to the screening window for participants to complete a second round of urine collection. Should potential participants again fail to achieve the within-20% variation, they will be excluded from participation.
5. Estimated GFR at screening ≥ 30 mL/min normalized to 1.73 m^2 BSA, calculated using the CKD-EPI equation in participants aged ≥ 18 years ([Levey & Stevens, 2010](#)) or the multivariate equation by Schwartz in participants aged 6 to 17 years ([Schwartz et al., 2012](#))

Sex

6. Male or female

Male participants:

A male participant with a female partner of childbearing potential must agree to use contraception, as detailed in Section 10.4.2, during the treatment period and for at least 12 weeks after the last dose of study intervention and refrain from donating sperm during this period.

Female participants:

A female participant is eligible to participate if she is not pregnant (see Section 10.4.1), not breastfeeding, and at least 1 of the following conditions applies:

Not a woman of childbearing potential (WOCBP) as defined in Section 10.4.1

OR

A WOCBP who agrees to follow the contraceptive guidance in Section 10.4.2 during the treatment period and for at least 12 weeks after the last dose of study intervention.

Contraceptive use by men or women should be consistent with local regulations regarding the methods of contraception for those participating in clinical studies.

Informed Consent/Assent

7. Participant (and/or participant's parent or legal guardian if participant is a minor [defined as patient < 18 years of age, or younger than the age of majority, according to local regulations]) is capable of giving signed informed consent, which includes compliance with the requirements and restrictions listed in the informed consent form (ICF) and in this protocol.
 - a. Adolescents (12 to < 18 years of age, or older than 12 years but younger than the age of majority, according to local regulations) must be able to provide written assent for participation.
 - b. For children younger than 12 years of age, assent will be based on local regulations.

5.2. EXCLUSION CRITERIA

An individual who meets any of the following criteria will be excluded from participation in this study:

Medical Conditions

1. Prior renal or hepatic transplantation, or planned transplantation within the study period
2. Currently receiving dialysis, or anticipating requirement for dialysis during the study period
3. Plasma oxalate > 30 $\mu\text{mol/L}$
4. Documented evidence of clinical manifestations of systemic oxalosis (including pre-existing retinal, heart, or skin calcifications, or history of severe bone pain, pathological fractures, or bone deformations)
5. Presence of any condition or comorbidities that would interfere with study compliance or data interpretation or potentially impact patient safety including, but not restricted to:
 - a. severe intercurrent illness
 - b. known causes of active liver disease/injury or transaminase elevation (e.g., alcoholic liver disease, nonalcoholic fatty liver disease/steatohepatitis)

- c. physician concerns about intake of drugs of abuse or excessive alcohol intake, or history of excessive alcohol intake in the 2 years prior to enrollment (defined as ≥ 21 units of alcohol per week in men and ≥ 14 units of alcohol per week in women; where a "unit" of alcohol is equivalent to a 12-ounce beer, 4-ounce glass of wine, or 1-ounce shot of hard liquor)
- d. history of serious mental illness that includes, but is not limited to, schizophrenia, bipolar disorder, or severe depression requiring hospitalization or pharmacological intervention
- e. clinically relevant history or presence of cardiovascular, respiratory, gastrointestinal, hematological, lymphatic, neurological, musculoskeletal, genitourinary, immunological diseases, including dermatological (e.g., rash, severe eczema or dermatitis), or connective tissue diseases or disorders

Prior/Concomitant Therapy

6. Use of an RNA interference (RNAi) drug within the last 6 months
7. History of one or more of the following reactions to an oligonucleotide-based therapy:
 - a. severe thrombocytopenia (platelet count $\leq 100,000/\mu\text{L}$)
 - b. hepatotoxicity, defined as alanine aminotransferase (ALT) or aspartate aminotransferase (AST) > 3 times the upper limit of normal (ULN) and total bilirubin $> 2 \times \text{ULN}$ or international normalized ratio (INR) > 1.5
 - c. severe flu-like symptoms leading to discontinuation of therapy
 - d. localized skin reaction from the injection (graded severe) leading to discontinuation of therapy
 - e. coagulopathy/clinically significant prolongation of clotting time
8. Participants receiving pyridoxine must have been at a stable dose for at least 4 weeks prior to Day 1 and must be willing to remain on the same stable dose throughout the study.

Prior/Concurrent Clinical Study Experience

9. Participation in any clinical study in which they received an investigational medicinal product (IMP) within 4 months before Screening
 - a. for IMPs with the potential to reduce urine and/or plasma oxalate concentrations, these concentrations must have returned to historical baseline levels prior to Screening

Diagnostic assessments

10. Liver function test abnormalities: ALT and/or AST $> 1.5 \times \text{ULN}$ for age and gender
11. Positive screening for hepatitis B surface antigen (HBsAg), anti-hepatitis C virus (HCV) antibodies, or anti-human immunodeficiency virus (HIV) 1 and 2 antibodies. If participant has been tested in the past 3 months, medical record documentation of this testing can be used for screening. Viral serology testing not required in participants < 18 years of age.

12. Positive urine drug screen (to include at minimum: amphetamines, barbiturates, cocaine, opiates, and benzodiazepines). Investigator discretion is allowed. Urine drug screening is not required in participants ≤ 12 years of age.

Other Exclusions

13. Known hypersensitivity to DCR-PHXC, or any of its ingredients
14. Inability or unwillingness to comply with the specified study procedures, including collection of 24-hour urine samples, and the lifestyle considerations detailed in Section 5.3

5.3. LIFESTYLE CONSIDERATIONS

During this study, participants are asked to:

- refrain taking vitamin C supplements, including multivitamins, for 24 hours prior to and during the 24-hour urine specimen collections
- avoid oxalate-rich foods
- abstain from strenuous exercise for 24 hours before each blood collection for clinical laboratory tests
- continue to follow standard of care for PH, including, but not limited to hyperhydration regimens, oral potassium citrate administration, and treatment with vitamin B6 (if applicable).

5.4. SCREEN FAILURES

Screen failures are defined as participants who consent to participate in the clinical trial but are not subsequently randomly assigned to the study intervention or entered in the study. A minimal set of screen failure information is required to ensure transparent reporting of screen failure participants, to meet the Consolidated Standards of Reporting Trials (CONSORT) publishing requirements and to respond to queries from regulatory authorities. Minimal information includes demography, screen failure details, eligibility criteria, and any SAEs.

Rescreened participants will be assigned a new participant number for re-screening. Potential participants may undergo rescreening only with approval of the Sponsor.

5.5. STRATEGIES FOR RECRUITMENT AND RETENTION

Given the rare-disease nature of PH, potential participants may be under the care of the Investigator. Others may be referred to the clinical site by their treating physicians, or through other patient networks.

Participants will be reimbursed for expenses associated with study visits, such as parking, transportation, and meals. For car travel, mileage will be reimbursed at the current regional government rate. Participants must submit supporting documentation for the reimbursement(s) requested.

6. STUDY INTERVENTION

6.1. STUDY INTERVENTION(S) ADMINISTRATION

6.1.1. Study Intervention Description

DCR-PHXC is a synthetic RNAi drug that consists of a double-stranded oligonucleotide conjugated to GalNAc ligands. DCR-PHXC is a sterile formulation of the drug substance (DCR-L1360) in WFI, intended for SC administration.

DCR-PHXC is not commercially available in any country.

The placebo comparator is 0.9% normal saline for injection.

6.1.2. Dosing and Administration

Study intervention will be administered in clinic as a SC injection into the abdomen or thigh using a 25- to 27-gauge needle, 3/8 to 5/8 inches long.

In adults and in adolescents (aged 12-17 years) weighing ≥ 50 kg, study intervention will be administered once monthly at a dose of 170 mg DCR-PHXC (or the equivalent volume of placebo). In adults and adolescents weighing < 50 kg, study intervention will be administered once monthly at a dose of 136 mg DCR-PHXC (or the equivalent volume of placebo).

Participants who begin the study weighing less than 50 kg will have their dose increased to the 170 mg dose should they reach the 50 kg threshold. Participants receiving the 170 mg dose will not have their dose decreased to the 136 mg dose should they fall below the 50 kg threshold.

The dose for participants aged 6 to 11 years will be 3.5 mg/kg monthly, not to exceed 136 mg. The total dose for 6- to 11-year-old participants will be based upon body weight recorded on study Day 1 and will be constant throughout the study, regardless of any weight gain or loss or change in age (i.e. an 11-year-old turns 12 during the study). The volume of a single injection should not exceed 0.5 mL. Should the calculated dose require a volume greater than 0.5 mL, the dose should be administered in 2 equally divided injections.

An unblinded pharmacist or designee will prepare the dose of DCR-PHXC or placebo as detailed in Section **6.2.4**.

To prevent any blinded site staff or study participants from visually observing color differences between DCR-PHXC and placebo, syringes will be tinted or shrouded to mask the color difference.

6.2. PREPARATION/HANDLING/STORAGE/ACCOUNTABILITY

6.2.1. Acquisition and Accountability

DCR-PHXC will be provided to the site pharmacy by the Sponsor. Study intervention accountability records will be maintained by an unblinded pharmacist or designee to maintain the study blind, and an unblinded study monitor will be employed to review accountability records.

The placebo control will be supplied by the site pharmacy.

6.2.2. Formulation, Appearance, Packaging, and Labeling

DCR-PHXC is a colorless to pale yellow, preservative-free, sterile solution of DCR-L1360 at a concentration of 170 mg/mL in WFI. The product is filled into clear Type-I 2-mL glass vials sealed with Flurotec-coated chlorobutyl rubber stoppers with aluminum flip-off overseals. Each vial is intended for single use and contains an extractable volume of not less than 0.5 mL of DCR-PHXC. Each vial is labeled with a booklet label or a single panel label that contains country-specific related information, in compliance with regulatory and safety requirements.

The placebo comparator is 0.9% sterile normal saline for injection provided by the study site.

6.2.3. Product Storage and Stability

DCR-PHXC is to be stored at 2°C to 8°C (inclusive). DCR-PHXC is to be stored in an appropriately secured location in a refrigerator, and storage must comply with institutional procedures in effect at the study site for handling investigational products. Access must be limited to authorized clinic personnel. A temperature log will be maintained.

The placebo comparator should be stored in accordance with the product labeling.

6.2.4. Preparation

Study intervention will be prepared by the unblinded pharmacist or designee.

A second medically qualified person must check the dose preparation prior to administration to be sure the correct dose has been prepared.

The product should be allowed to warm to room temperature for approximately 1 hour but no more than 4 hours before administration.

6.3. MEASURES TO MINIMIZE BIAS: RANDOMIZATION AND BLINDING

This is a double-blind study in which treatment assignment will be blinded for the Investigators and any personnel (other than the unblinded pharmacist or designee) involved with the study conduct or evaluation at the investigational sites, the CRO, and the Sponsor.

All participants will be centrally assigned to randomized study intervention using an Interactive Web Response System (IWRS). Before the study is initiated, the log in information and directions for the IWRS will be provided to each site.

The randomization scheme will only be disclosed to selected personnel to ensure correct preparation of the study drug, correct set-up of the IWRS, safety monitoring by the DSMC, and expedited adverse reaction reporting. All aspects of blinding and unblinding for the study is outlined in the study-specific Blinding and Unblinding Plan.

Unblinding, i.e., breaking the code for an individual patient during the study, is restricted to emergency situations and should only be used under circumstances where knowledge of the treatment is necessary for the proper handling of the participant. The decision to break the code must be made by the Investigator. The study monitor and Sponsor must be informed about the code break as soon as possible. Detailed unblinding procedures are provided in a separate IWRS manual.

As DCR-PHXC is colorless to pale-yellow, an unblinded pharmacist or designee will prepare the syringes for delivery to the Investigator. To prevent any blinded site staff or study participants

from visually observing color differences between DCR-PHXC and placebo, syringes will be tinted or shrouded to mask the color difference.

Results of on-treatment 24-hour Uox measurements will not be returned to the Investigator prior to closure of the study, so as not to potentially unblind the study.

6.4. STUDY INTERVENTION COMPLIANCE

Study intervention will be administered by a member of the study staff.

6.5. CONCOMITANT THERAPY

For this protocol, a prescription medication is defined as a medication that can be prescribed only by a properly authorized/licensed clinician. Concomitant therapies to be recorded in the case report form (CRF) at every visit include concomitant prescription medications, over-the-counter medications, and supplements.

Participants taking pyridoxine (vitamin B6) must have been at a stable dose for at least 4 weeks prior to Day 1 and must remain on the same stable dose throughout the study.

Participants should avoid taking vitamin C supplements, including multivitamins, for 24 hours prior to and during the collection of 24-hour urine samples.

6.5.1. Rescue Medicine

Not applicable.

6.6. DOSE MODIFICATION

No dose modifications are allowed, other than those described in Section 6.1.2.

6.7. INTERVENTION AFTER THE END OF THE STUDY

In order to provide continued patient access to DCR-PHXC and to expand the safety database for the product, a roll-over long-term extension study is planned (DCR-PHXC-301). Participants may be screened for entry into the roll-over study when all DCR-PHXC-201 study assessments have been completed; including confirmation that the Day 180/EOS 24-hour urine collection satisfies the urine-collection completeness criteria. Participants not eligible for, or electing not to roll over into, Study DCR-PHXC-301 will be followed until Uox returns to $\geq 80\%$ of baseline. Hematology, clinical chemistry, urinalysis, and pregnancy testing (as detailed in **Table 3**), and 24-hour urine collections will be repeated monthly. Should this follow-up take more than 6 months, participants will be re-consented for additional follow-up.

7. STUDY INTERVENTION DISCONTINUATION AND PARTICIPANT DISCONTINUATION/WITHDRAWAL

7.1. DISCONTINUATION OF STUDY INTERVENTION

Study intervention for an individual participant may be permanently discontinued at any time at the discretion of the Investigator.

Study intervention for an individual participant must be temporarily interrupted and may be permanently discontinued for the following, as determined by the DSMC:

- any severe AE possibly, probably, or definitely related to study intervention

Study intervention for an individual participant will be permanently discontinued for any of the following:

- any SAE possibly, probably or definitely related to study intervention
- any of the changes in hepatic function detailed in Section 7.1.1
- pregnancy, as detailed in Section 10.4

Re-challenge with study intervention is not allowed.

Discontinuation from study intervention does not mean discontinuation from the study.

Remaining visits and study procedures should be completed as indicated by the SoA.

Additionally, participants in whom study intervention is prematurely discontinued will be followed until Uox returns to $\geq 80\%$ of baseline. Hematology, clinical chemistry, urinalysis, and pregnancy testing (as detailed in **Table 3**) and 24-hour urine collections will be repeated monthly. Should this follow-up take more than 6 months, participants will be re-consented for additional follow-up.

7.1.1. Drug-Induced Liver Injury Monitoring

Safety laboratory test results will be monitored by a central laboratory in real time with potential drug-induced liver injury (DILI) alerts sent to the Investigator.

For participants with normal liver biochemistries at baseline:

- **Close Monitoring:** An increase of serum ALT or AST to $> 3 \times$ ULN should be followed by repeat testing of ALT, AST, alkaline phosphatase, and total bilirubin within 48 to 72 hours to confirm the abnormalities and to determine if they are increasing or decreasing. Inquiry should also be made about symptoms, strenuous exercise, or previous seizures. Repeat testing 2 or 3 times weekly is recommended. All participants showing possible DILI should be followed until abnormalities return to normal or to the baseline state. If a participant lives remote from the study site, local testing may be performed, and the test results reported to the Investigator (along with the reference ranges for the local laboratory).
- **Study Intervention Discontinuation:** Study intervention will be discontinued when a participant meets one of the conditions outlined below (from 2009 FDA Guidance for Industry-Drug Induced Liver Injury: Premarketing Clinical Evaluation), or if the Investigator believes that it is in best interest of the participant. Safety laboratory

parameters will be monitored by a central laboratory in real time, with potential drug-induced liver injury (DILI) alerts sent to the Investigator.

- ALT or AST $> 8 \times$ ULN
- ALT or AST $> 5 \times$ ULN for more than 2 weeks
- ALT or AST $> 3 \times$ ULN and (total bilirubin $> 2 \times$ ULN or INR > 1.5)
- ALT or AST $> 3 \times$ ULN with the appearance of fatigue, nausea, vomiting, right upper quadrant pain or tenderness, fever, rash, and/or eosinophilia ($> 5\%$)

Close monitoring should be continued. Discontinuation from study intervention does not mean discontinuation from the study, and remaining study procedures should be completed as indicated by the SoA. Participants should be followed until Uox returns to $\geq 80\%$ of baseline.

Patients should be monitored at each study visit and instructed to call the Investigator for new or worsening symptoms of clinical hepatitis. Both symptoms and calls should be captured in dedicated CRFs.

For participants with elevated transaminases at baseline: The following Alternative DILI Monitoring Algorithm should be used.

- **Close Monitoring:** If participants develop elevations of AST or ALT > 2 times the screening value or total bilirubin > 1.5 times the screening value while on study, testing should be repeated within 48 to 72 hours. Persistent elevations should be followed by repeat testing and physical examination 2 to 3 times per week with or without study intervention discontinuation (see below).
- **Study Intervention Discontinuation:** Study intervention will be discontinued for abnormal liver function when a participant meets the following condition. Close monitoring should be continued. If a participant's home is remote from the study site, local testing may be performed, and the test results reported to the Investigator (along with the reference ranges for the local laboratory).
 - ALT or AST $> 5 \times$ the screening value in participants with the screening value $< 2 \times$ ULN

Discontinuation from study intervention does not mean discontinuation from the study, and remaining study procedures should be completed as indicated by the SoA. Participants should be followed until Uox returns to $\geq 80\%$ of baseline.

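### A participant whose rising liver enzyme was slightly raised at screening has no mandatory stop for ALT/AST above 3×ULN with raised bilirubin or INR

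*Protocol*

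**What the plan says.** Protocol 7.1.1 contains two algorithms, chosen by baseline liver status.

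- **Normal liver biochemistries at baseline.** There are four mandatory stops: ALT or AST above 8×ULN; above 5×ULN for more than 2 weeks; above 3×ULN with listed symptoms or eosinophilia; and the combined criterion, "ALT or AST $> 3 \times$ ULN and (total bilirubin $> 2 \times$ ULN or INR > 1.5").
- **Raised transaminases at baseline.** "For participants with elevated transaminases at baseline: The following Alternative DILI Monitoring Algorithm should be used". On stopping it says "Study intervention will be discontinued for abnormal liver function when a participant meets the following condition", and one condition follows: "ALT or AST $> 5 \times$ the screening value in participants" whose screening value was below 2×ULN. Bilirubin appears only as a monitoring trigger, at more than 1.5 "times the screening value while on study, testing should be repeated within 48 to 72 hours". INR does not appear. Persistent elevations are followed closely, whether or not dosing is stopped.

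Protocol 5.2 settles who can fall under the second algorithm. Exclusion 10 ("Liver function test abnormalities: ALT and/or AST" above 1.5×ULN) leaves room for screening values above 1.0 and up to 1.5×ULN. Exclusion 5b narrows that group by removing "known causes of active liver disease/injury or transaminase elevation". Exclusion 7b concerns earlier reactions to oligonucleotide therapy and includes "hepatotoxicity, defined as alanine aminotransferase (ALT) or aspartate aminotransferase (AST) > 3 times the upper limit of normal (ULN) and total bilirubin" above 2×ULN or INR above 1.5.

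**The concern.** The same on-study result leads to different mandatory responses depending on a small difference at screening. A participant with normal baseline liver tests who reaches ALT 4×ULN with bilirubin 3×ULN must stop. One whose ALT screened at 1.1×ULN need not, because the alternative algorithm omits the combined criterion. The protocol itself labels this pattern hepatotoxicity, and the study drug is an oligonucleotide directed to hepatocytes.

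The protocol gives no reason for the omission, and a mildly raised baseline transaminase does not explain a bilirubin above 2×ULN or an INR above 1.5. The reference in Protocol 7.1 to the hepatic changes in 7.1.1 does not close the gap, since 7.1.1 confines the combined criterion to normal-baseline participants. What is at stake is participant safety; the primary endpoint, power and type I error are not affected.

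**Working it through.** The plan states no figure to reproduce here. The check expresses both rules in multiples of ULN.

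**Inputs**
- *s* = screening value of the enzyme that later rises, in ×ULN. If that enzyme was itself raised, 1.0 < *s* ≤ 1.5 (upper bound from exclusion 10, Protocol 5.2).
- Alternative algorithm (Protocol 7.1.1): enzyme monitoring trigger 2*s*; stop 5*s*.
- Normal-baseline combined stop (Protocol 7.1.1): ALT or AST above 3×ULN with bilirubin above 2×ULN or INR above 1.5.
- Test case: ALT 4×ULN with bilirubin 3×ULN (or INR 1.8).

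**Formulae**
- Uncovered ALT/AST window, when bilirubin or INR meets the combined criterion: from 3 up to 5*s*, width max(0, 5*s* − 3).
- Test ALT as a multiple of screening: 4/*s*.

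| *s* (×ULN) | Stop above 5*s* (×ULN) | Window (×ULN) | Width | 4/*s* |
|---|---|---|---|---|
| just over 1.0 | 5.0 | 3.0–5.0 | 2.0 | 4.0 |
| 1.2 | 6.0 | 3.0–6.0 | 3.0 | 3.3 |
| 1.5 | 7.5 | 3.0–7.5 | 4.5 | 2.7 |

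Across this range 4/*s* runs from 2.7 to 4.0. It is always above the twofold monitoring trigger and never above the fivefold stop, whatever the bilirubin or INR. Under the normal-baseline rule the same result stops dosing, since 4 > 3 and 3 > 2 (or 1.8 > 1.5).

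**Where the gap ends.** The stop is specific to each enzyme, so someone placed in this algorithm because only the other enzyme was raised may be covered. There is no gap when 5*s* ≤ 3, that is *s* ≤ 0.6. ALT 4×ULN stops dosing when 4 > 5*s*, that is *s* < 0.8.

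**Effect of adding the combined criterion.** The test case becomes a mandatory stop for every *s*. At *s* = 1.5, 3×ULN is 3/1.5 = 2.0 times screening, so the enzyme limb alone is modest there, but the criterion also requires raised bilirubin or INR.

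**The case against.** The alternative algorithm is not weaker throughout. For this group its enzyme-only stop acts at once above 5.0 to 7.5×ULN, whereas the normal-baseline rule waits for more than 8×ULN, or more than 5×ULN for over 2 weeks. With *s* = 1.2, ALT 7×ULN stops dosing immediately (7 > 6). Its enzyme monitoring trigger, 2.0 to 3.0×ULN, comes no later than the normal-baseline trigger of 3×ULN, and it adds a bilirubin-only retest.

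Dosing is monthly (Protocol 6.1.2), so there is usually time to decide before the next dose. Meanwhile there are repeat tests within 48 to 72 hours, testing and examination two to three times weekly if the elevation persists, real-time laboratory alerts, and Medical Monitor and DSMC review. INR is measured at scheduled visits, although Appendix A allows coagulation samples to be omitted.

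Other routes to stopping exist. A related SAE requires permanent discontinuation, and Protocol 10.3.2 says important medical events should usually be treated as serious. A related severe AE requires interruption. Protocol 7.2 lets the investigator withdraw a participant who newly meets an exclusion criterion (arguably 7b) or whose interests require it, and Protocol 7.1 allows a discretionary stop at any time.

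All of this stands, and it limits the weight of the point. None of it supplies a mandatory stop for the pattern. Seriousness needs medical judgement unless a listed outcome such as hospitalisation occurs. In Protocol 10.3.4, severe means preventing normal everyday activities, which an asymptomatic laboratory pattern may not do. Even a possible relationship requires that the participant's condition is an unlikely explanation, and a pre-existing enzyme elevation invites that explanation.

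**Conclusion.** The concern holds as a gap in one criterion. When the rising enzyme screened above 1.0 and up to 1.5×ULN, ALT or AST above 3×ULN and up to 5.0–7.5×ULN, with bilirubin above 2×ULN or INR above 1.5, carries no mandatory liver-test stop. Participants are monitored, but whether dosing stops rests on classification or discretion.

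The number affected is unknown, probably small and possibly zero: 36 evaluable participants are planned, 24 of them on active drug, and exclusion 5b removes known causes of raised transaminases. The point should be fixed because the outcome is serious and the remedy cheap, not because many participants are expected to be exposed.

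Two assumptions apply. Raised at baseline is read as above ULN, since 7.1.1 gives no number. The baseline that selects the algorithm is taken to be the screening value its thresholds use; a participant raised at screening but normal before dosing on Day 1 might instead be placed under the normal-baseline rule.

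**What to change.** Add to the discontinuation list of the alternative algorithm in Protocol 7.1.1: ALT or AST >3×ULN and (total bilirubin >2×ULN or INR >1.5). Keep the existing stop at more than 5 times screening, and align the central-laboratory liver alerts with the revised list. A symptom-based stop (set relative to baseline) and a 2-week duration stop could also be considered but are not needed to close this gap.

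The cost is one line of protocol text and an update to alert programming, with no extra visits or patients. A few more participants may meet a mandatory stop, and it would be permanent because Protocol 7.1 does not allow re-challenge. Requiring raised bilirubin or INR as well keeps that number low.
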